8.2.2 Specific ocular tests

Specific complete ocular tests at baseline and EOT will include: assessment of ocular/visual symptoms and ocular exams including visual acuity, slit lamp under dilatation, and Schirmer's test.

Standard specific ocular tests include:

- Assessment of ocular/visual symptoms, (ie, blurred vision, photophobia, dry eye, etc) at each visit before each study intervention. Start and end dates of symptoms will be collected.
- Visual acuity at baseline and whenever clinically indicated.
- Slit lamp under dilatation at screening and whenever clinically indicated.
- Schirmer's test at baseline and whenever clinically indicated.

In participants with any ocular/visual symptom (eg, blurred vision, photophobia), complete ocular tests will be repeated at the time of the occurrence of the ocular toxicity, if any, regardless of the grade. Thereafter, visual acuity, slit lamp examination under dilatation, and Schirmer's test will be repeated once weekly (if not recommended to have less frequent assessment by ophthalmologist based on lesion characteristics) until resolution to Grade 1. In case of recurrent ocular toxicity observed in subsequent cycles, visual acuity and slit lamp examination under dilatation, and Schirmer's test will be performed at the time of the event onset, then weekly until resolution to Grade 1.

8.2.3 Vital signs

- Temperature, pulse rate, and blood pressure will be assessed during each physical examination.
- Blood pressure and pulse measurements will be assessed with a completely automated device. Manual techniques will be used only if an automated device is not available.
- Blood pressure and pulse measurements should be preceded by at least 5 minutes of rest for the participant in a quiet setting without distractions (eg, television, cell phones).
- Vital signs (to be taken before blood collection for laboratory tests) will consist of 1 pulse and 3 blood pressure measurements (3 consecutive blood pressure readings will be recorded at intervals of at least 1 minute). The average of the 3 blood pressure readings will be recorded.

8.2.4 Electrocardiograms

- Single 12-lead ECGs will be obtained as outlined in the SoA (see [Section 1.3](#)) using an ECG machine that automatically calculates the heart rate and measures PR, QRS, and QT intervals.
- ECG is required at screening within 7 days prior IMP administration, at baseline before starting and after completing the first IMP administration (within 30 minutes after the end of tusamitamab ravtansine infusion); before IMP administration at each cycle; and at the End of treatment evaluation, 30 (± 5) days after last IMP administration. This test can be performed on the same day before the study intervention administration, or on the day before. An ECG is to be repeated as clinically indicated.
- ECGs will be interpreted by a qualified physician at the site as soon after the time of ECG collection as possible, and ideally while the patient is still present, should additional ECGs be performed or for immediate patient management should any clinically relevant findings be identified.

8.2.5 Echocardiogram or MUGA scan

An echocardiogram or multigated acquisition (MUGA) scan to evaluate left ventricular ejection fraction (LVEF) will be evaluated during screening period, and whenever clinically indicated.

8.2.6 Clinical safety laboratory assessments

- See Appendix 2 ([Section 10.2](#)) for the list of clinical laboratory tests to be performed and to the SoA ([Section 1.3](#)) for the timing and frequency. These tests will be done at each cycle; during the first 2 cycles, hematology and liver function tests will be assessed weekly.
- If Grade 4 neutropenia occurs, assess ANC every 2 to 3 days until $ANC \geq 0.5 \times 10^9/L$.
- In case of Grade ≥ 3 abnormal liver function tests, additional tests will be done every 2 to 3 days until recovery to the baseline value. Additional tests will be performed when clinically appropriate. This test can be performed before the study intervention administration on the same day or the day before.
- The Investigator must review the laboratory report, document this review, and record any clinically significant changes occurring during the study as an AE. The laboratory reports must be filed with the source documents. Abnormal laboratory findings associated with the underlying disease are not considered clinically significant, unless judged by the Investigator to be more severe than expected for the participant's condition.
- All laboratory tests with values considered clinically significantly abnormal during participation in the study or within 30 days after the last dose of study intervention should be repeated until the values return to normal or baseline or are no longer considered clinically significant by the Investigator.
 - If clinically significant values do not return to normal/baseline within a period of time judged reasonable by the Investigator, the etiology should be identified and the Sponsor notified.
 - All protocol-required laboratory tests, as defined in Appendix 2 ([Section 10.2](#)), must be conducted in accordance with the laboratory manual and the SoA ([Section 1.3](#)).
 - If laboratory values from non-protocol-specified laboratory tests performed at the institution's local laboratory require a change in participant management or are considered clinically significant by the Investigator (eg, SAE or AE or dose modification), then the results must be recorded.

8.2.7 Guidelines for management of adverse events

Management of AEs related to tusamitamab ravtansine and ramucirumab is summarized in Appendix 6 ([Section 10.6](#)); for specific AE related to ramucirumab intake, please refer to the current prescribing information leaflet; the most relevant reported events are summarized in this section as reminder.

8.2.7.1 Hypersensitivity reactions

Premedication treatments provided as prophylactic treatment for hypersensitivity reactions are detailed in [Section 6.1](#).

In case of an event of hypersensitivity reaction, please refer to the recommended dose modification or discontinuation table in Appendix 6 ([Section 10.6](#)).

As with other monoclonal antibodies, IRRs may occur during or following ramucirumab or tusamitamab ravtansine administration. Patients should be closely monitored for signs and symptoms indicative of an IRR from the initiation of the infusion in an area where resuscitation equipment and other agents (such as epinephrine and corticosteroids) are readily available.

A 1 hour observation period following the ramucirumab infusion is mandatory for the first 2 infusions. If the patient shows no evidence of an IRR with the first 2 infusions of ramucirumab, no observation period is required for subsequent infusions. In the event an IRR occurs thereafter, the 1 hour observation should be reinstated. Symptoms of IRRs include rigors/tremors, back pain/spasms, chest pain and/or tightness, chills, flushing, dyspnea, wheezing, hypoxia, and paresthesia. In severe cases, symptoms include bronchospasm, supraventricular tachycardia, and hypotension. If the patient experiences a Grade 1 or Grade 2 IRR, interrupt the infusion and treat the patient with anti-allergic medication. If symptoms resolve, resume the infusion at a reduced rate (50%).

8.2.7.2 Ocular toxicity

It is recommended that topical artificial tears (and/or hyaluronic ophthalmic gel) are used regularly in all patients treated with tusamitamab ravtansine during the study treatment period.

The patient should be asked about ocular/visual symptoms at each visit, and ocular evaluation including visual acuity, slit lamp examination under dilatation, and Schirmer's test should be carried on according to Study Procedures ([Section 8.2.2](#)). Ocular evaluation will be performed at baseline (during the screening period), as required during the treatment (ie, on occurrence of ocular symptoms such as blurred vision, photophobia, pain), at the EOT visit, and when relevant at follow-up visit(s). The outcome of the examination should be available before infusion of the next cycle. If ocular symptoms are present, then a formal ocular examination should be performed. In patients with any ocular/visual symptom(s) (eg, blurred vision, photophobia), the ocular evaluation should be repeated once weekly, unless less frequent assessment is recommended by an ophthalmologist, until resolution to Grade 1. Subsequently, the participant should be followed with ocular exam (slit lamp and visual acuity) at each cycle until total resolution of the event.

Photographs of the cornea are recommended to be taken at the site, if possible, when ocular findings are first documented, and to follow progression when relevant. Tonometry and additional ocular assessment can be performed at discretion of an ophthalmologist when applicable.

8.2.7.2.1 Keratopathy/keratitis management

Reversible non-inflammatory, microcystic keratopathy was identified as the DLT during the dose escalation process in study TED13751 with tusamitamab ravtansine. At slit-lamp examination, it presents as lesions consisting of 100s to 1000s microcysts and/or deposits that are initially observed at the periphery of the cornea, the limbus being preserved. The lesions have a centripetal distribution and evolve towards the center of the corneal upon resolution, following the natural keratinocyte regeneration process.

For standardization of AE verbatim, keratopathy should be preferred term unless otherwise specified by an ophthalmologist due to inflammatory findings on eye exams leading to diagnosis of keratitis.

The potential ocular/visual toxicity symptoms could include, but are not limited to, blurred vision, dry eye, and photophobia. Curative treatment may be used as recommended by an ophthalmologist.

No primary prophylaxis other than prevention of dry eye with artificial tears and/or hyaluronic ophthalmic gel is recommended; the use of contact lenses is not permitted during the treatment period. Corticosteroid-containing ocular drugs are recommended for the management of keratopathy/keratitis in the case that ocular symptoms occur, and treatment will be performed based on discretion of ophthalmologist. Dose modification and recommendations are further described in Appendix 6 ([Section 10.6](#)).

After resuming study treatment, a patient who had Grade ≥ 2 keratopathy/keratitis should be followed with standard ocular exams (ie, slit lamp examination under dilatation and visual acuity) every 2 cycles, even if symptoms are no longer reported. If no event recurs during the next 4 cycles, then regular follow-up (ie, symptom assessment at each visit with standard ocular exam in case of any ocular sign/symptom) is applied.

8.2.7.3 Management of anemia

Close surveillance of any signs and symptoms is required: a routine blood hematology workup, including red blood cell (RBC) counts, hemoglobin, hematocrit, WBC with differential, and platelet counts will be done weekly during the first 2 cycles, and thereafter each treatment cycle before IMP administration. Patients should not start Cycle 1 treatment if hemoglobin is < 9.0 g/dL. To be eligible for the study and to receive the first study treatment, the participant must have been transfusion-free for 2 weeks. During the treatment period, erythrocyte transfusion can be given, upon Investigator decision. Erythropoietin can be given at the discretion of the Investigator, except during Screening and the first 2 cycles. Cycle delays or modifications should be compliant with Appendix 6 ([Section 10.6](#)).

8.2.7.4 Management of neutropenia

In patients who experienced either Grade 3 or 4 febrile neutropenia or Grade 4 decreased neutrophil count (< 500 cells/mm³) for more than 1 week during study intervention, prophylactic G-CSF should be implemented per ASCO guidelines (13) to ensure dose intensity (Appendix 6, [Section 10.6](#)). Doses of tusamitamab ravtansine should be reduced in case of recurrent events even after prophylactic G-CSF use.

If the patient continues to experience these reactions at a lowered dose, the treatment should be discontinued ([Section 7.1](#)).

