Neutrophil count decreased (continued)	Grade 4 >7 days <500/mm ³ ; <0.5 × 10 ⁹ /L	Delay the cycle until absolute neutrophil count >1500/mm ³ . 1st episode administer next cycle with ramucirumab at the same dose and administer growth factors 2nd episode: administer ramucirumab at the same dose 3rd episode: definitive discontinuation of IMPs	Delay the cycle until absolute neutrophil count >1500/mm ³ . 1 st episode administer tusamitamab ravtansine next cycle at the same dose and administer growth factors 2 nd episode: administer tusamitamab ravtansine at reduced dose 3 rd episode: definitive discontinuation	Follow ASCO guidelines on G-CSF usage and antibiotherapy (13). Repeat test every 3 days.
Febrile neutropenia	Grade 3 Absolute neutrophil count <1000/mm ³ with a single temperature of >38.3°C (101°F) or a sustained temperature of ≥38°C (100.4°F) for more than 1 hour	Delay cycle until absolute neutrophil count >1500/mm ³ . 1st episode administer next cycle at the same dose and administer G-CSF 2nd episode: administer ramucirumab at reduce dose 3rd episode: definitive discontinuation	Delay cycle until absolute neutrophil count >1500/mm ³ . 1 st episode administer next cycle at the same dose and administer G-CSF 2 nd episode: administer tusamitamab ravtansine at reduce dose 3 rd episode: definitive discontinuation	To ensure relative dose intensity, G-CSF is recommended as secondary prophylaxis in all patients with Grade 3 febrile neutropenia ASCO guideline is recommended for supportive treatment if there are no defined clinical standards (13).
	Grade 4 Life-threatening consequences	Administration changes to be decided at the Investigator's discretion per product label	Administration changes to be decided at the Investigator's discretion. 1 st episode: administer next cycle at reduced dose and administer G-CSF 2 nd episode: definitive discontinuation	
Hypertension	Grade 3 Severe hypertension	Withhold ramucirumab until controlled with medical management, and restart at same dose	Administer tusamitamab ravtansine the same day as ramucirumab	
	Grade 4 Severe hypertension that cannot be controlled with antihypertensive therapy	Definitively discontinue ramucirumab	Administer tusamitamab ravtansine as planned	

Event	Symptoms severity (Nadir) (NCI CTCAE v5)	Management of IMP dosing (ramucirumab)	Management of IMP dosing (tusamitamab ravtansine)	Supportive care guidelines

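### For Grade 4 febrile neutropenia, Section 8.2.7.4 and Appendix 6 give different tusamitamab ravtansine instructions, and the Appendix 6 cell combines Investigator discretion with a fixed schedule

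*Protocol*

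**What the plan says.** **Section 8.2.7.4 (management of neutropenia).** The section covers participants with "either Grade 3 or 4 febrile neutropenia or Grade 4 decreased neutrophil count" lasting more than a week. Three statements follow:

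- After the event, "prophylactic G-CSF should be implemented per ASCO guidelines (13) to ensure dose intensity".
- Then: "Doses of tusamitamab ravtansine should be reduced in case of recurrent events even after prophylactic G-CSF use".
- Finally: "If the patient continues to experience these reactions at a lowered dose, the treatment should be discontinued".

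**Appendix 6 (Section 10.6), Grade 4 febrile neutropenia, tusamitamab ravtansine column.** The cell opens with "Administration changes to be decided at the Investigator's discretion". It then sets a schedule. For the first episode it says "administer next cycle at reduced dose and administer G-CSF"; for the second, the drug is stopped permanently. The ramucirumab cell beside it gives only discretion, by reference to the product label, so the inconsistency concerns tusamitamab ravtansine.

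**Which text leads.** Section 6.5 sends cycle delays, dose modifications and discontinuation to Appendix 6. The opening of Section 8.2.7 says that management of adverse events for both drugs is summarized there. Section 8.2.7.4 also cites Appendix 6.

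**Limits on dosing.** Table 7 in Section 6.5 gives tusamitamab ravtansine one reduction step and marks a second as not permitted. Section 6.5 adds that a participant already reduced once, who has an event that would call for another reduction, must be discontinued.

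**The concern.** Appendix 6 labels Grade 4 febrile neutropenia as life-threatening. An investigator who looks up the next cycle after a first such event finds three statements. One section calls for G-CSF with no reduction mentioned, the appendix sets a reduced dose, and the sentence above that schedule leaves changes to judgement. Section 6.5 also requires Sponsor consultation for modifications that differ from the protocol, unless immediate safety requires them. An investigator who relies on the discretion sentence therefore cannot tell whether that is compliance or a departure.

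With only one reduction step available, the handling of a first episode can decide whether the participant stays on the drug. It also feeds descriptive outputs in the SAP: dose reductions (Section 3.6.1.2), adverse events leading to dose modification or discontinuation (Section 3.6.2, Table 8), and the predose and end-of-infusion concentrations excluded after a reduction (Section 3.7.1.1).

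**Working it through.** The point turns on wording, so the check sets the texts side by side for tusamitamab ravtansine.

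| Event | Section 8.2.7.4 | Appendix 6 |
|---|---|---|
| Grade 3 febrile neutropenia | G-CSF; reduce on recurrence after G-CSF; stop if events continue at the lowered dose | 1st: same dose plus G-CSF; 2nd: reduced dose; 3rd: stop |
| Grade 4 neutrophil decrease beyond a week | As above | 1st: same dose plus growth factors; 2nd: reduced dose; 3rd: stop |
| Grade 4 febrile neutropenia | As above | Discretion; 1st: reduced dose plus G-CSF; 2nd: stop |

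**Step 1: where they agree.** In the first two rows the sequences match. For Grade 3 febrile neutropenia, for example, the appendix reaches "administer tusamitamab ravtansine at reduce dose" at the second episode. The difference is confined to Grade 4 febrile neutropenia.

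**Step 2: first Grade 4 episode.** Section 8.2.7.4 states G-CSF and no reduction, and gives preserving dose intensity as the aim. Appendix 6 states a reduction together with G-CSF. They differ by one step.

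**Step 3: second Grade 4 episode.** If the first episode was handled under Appendix 6, the participant is already at the lowered dose. A further event then leads to stopping under both texts. They diverge at the second episode only if the first was handled without a reduction: Section 8.2.7.4 would then reduce, and Appendix 6 would stop. The second-episode difference thus mostly follows from the first.

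**Step 4: effect of the single reduction step.** Take a participant already reduced once for another toxicity who has a first Grade 4 febrile neutropenia. The Appendix 6 schedule calls for a reduction that is no longer available, so Section 6.5 requires discontinuation. Section 8.2.7.4 states only G-CSF. The discretion sentence leaves the outcome open.

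**Step 5: does any rule settle it?** The referrals to Appendix 6 bear on the difference between sections. They cannot settle the relation between two statements inside one Appendix 6 cell. Section 6.5 has a most-conservative rule, but it is written for a participant with several adverse events whose recommendations conflict, not for two instructions on one event.

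**Step 6: how many participants.** The documents give no febrile neutropenia rate for this combination. The only figure is 2.4% serious febrile neutropenia with ramucirumab plus paclitaxel (Protocol Section 2.3.1). If that rate applied to the 32 to 38 treated participants in SAP Section 1.1:

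- 0.024 × 32 = 0.77
- 0.024 × 38 = 0.91

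That is about one participant. The figure spans grades, so Grade 4 would be a subset. It counts serious events only and comes from a different partner drug, so it is an order of magnitude, not an estimate.

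**The case against.** The strongest reply is that the protocol has a governing text. Section 6.5 and the opening of Section 8.2.7 both point to Appendix 6, so Section 8.2.7.4 can be read as a short summary, with Appendix 6 refining it by grade. Much of this stands, and it weakens Section 8.2.7.4 as a rival instruction. It does not remove the problem: neither text says which prevails where they differ, and the conflict within the cell remains.

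The discretion sentence can also be read compatibly. In the Grade 3 cell, the line above the episode list governs cycle delay. The Grade 4 sentence holds the same position, so it may concern timing while the episode lines set the dose. That reading is possible, but nothing in the cell says so.

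A reader might also infer stronger points that the documents do not support:

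- **That Section 8.2.7.4 forbids reduction at a first event.** It does not say so. Its sequence and its dose-intensity aim imply none, but that is an inference.
- **That the stopping rules conflict independently.** Step 3 shows that the difference mostly follows from the first episode.
- **That safety endpoints are affected.** The endpoints are DLTs, treatment-emergent and serious adverse events, and laboratory abnormalities. Dose-reduction and discontinuation counts are descriptive summaries.
- **That practice will vary by site.** The wording permits it; nothing in the documents shows it.

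**Conclusion.** The concern holds as an internal inconsistency limited to tusamitamab ravtansine after Grade 4 febrile neutropenia. It has two parts. The sections differ on a first episode, where the referrals favour Appendix 6 without saying that it prevails. And within the Appendix 6 cell, discretion and a fixed schedule stand together with no stated relation.

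The consequence for an individual can be large, because it may decide whether the drug continues. The number affected cannot be estimated for this combination; the borrowed 2.4% suggests about one participant or fewer. No endpoint definition or estimand depends on the cell, so the effect on the analysis is confined to descriptive summaries.

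This assumes that Table 7's limit of one tusamitamab ravtansine reduction applies. Section 6.5 also mentions a possible second reduction after case-by-case discussion with the Sponsor, but Table 7 provides a second step for ramucirumab only. No view is taken on which instruction is clinically right.

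**What to change.** Section 8.2.7.4 and the Appendix 6 Grade 4 febrile neutropenia cell must be reconciled to one consistent instruction for tusamitamab ravtansine. The reconciled text must state how the discretion sentence relates to the episode schedule. The choice of instruction belongs to the sponsor.

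The cost is a protocol clarification. Sample size, endpoints and planned analyses do not change.

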8.2.7.5 Liver function tests

Hepatic enzyme increase has been reported with tusamitamab ravtansine administration as monotherapy or ramucirumab. Patients should be carefully followed and in case of Grade ≥ 3 abnormal liver function tests, additional liver function tests will be done every 2 to 3 days until recovery to baseline value. tusamitamab ravtansine should be permanently discontinued in case of drug-induced Grade 4 liver enzyme increase. For stopping rules for ramucirumab administration, the current product leaflet should be followed.

Grade ≥ 3 (ie, $>5 \times$ ULN) increased liver enzyme events should be reported as AESIs.

8.2.7.6 Hypertension

An increased incidence of severe hypertension (CTCAE Grade 3) has been reported in patients receiving ramucirumab as compared with placebo. In most cases, hypertension was controlled using standard antihypertensive treatment. Preexisting hypertension should be controlled before starting ramucirumab treatment. Monitoring of blood pressure is required during ramucirumab therapy. Every attempt should be made to control blood pressure to systolic <140 mmHg and diastolic <90 mmHg prior to starting treatment with ramucirumab. Routine clinical and laboratory monitoring is required in patients who again develop hypertension or experience a deterioration in previous hypertension.

Withhold ramucirumab for severe hypertension until medically controlled. Permanently discontinue ramucirumab for medically significant hypertension that cannot be controlled with antihypertensive therapy or in patients with hypertensive crisis or hypertensive encephalopathy.

